or Level 4, respectively, when a single final week at the lower dose level is sufficient; see [Table 5](#)). The most common dosing scenarios that can be advanced to the Maintenance Period are shown in [Table 5](#). With concurrence of the medical monitor and the sponsor, some subjects may be allowed to enter the Maintenance Period at a lower dose (but not less than 100 mg BID) if tolerability is an issue after trying a higher dose (regardless of specific gravity result at the lower dose):

Table 5. Dosing Diagram in the Lixivaptan Titration Period

Dose Level	Week 1	Week 2	Week 3	Week 4	Week 5	Week 6
2	50 mg BID	100 mg BID	100 mg BID			
3	50 mg BID	100 mg BID	150 mg BID	150 mg BID		
3a	50 mg BID	100 mg BID	150 mg BID	150/100 mg (AM/PM)	150/100 mg (AM/PM)	
3a (when 2 nd week of Level 3 is not tolerated)	50 mg BID	100 mg BID	150 mg BID	150 mg BID	150/100 mg (AM/PM)	
4	50 mg BID	100 mg BID	150 mg BID	200 mg BID	200 mg BID	
4a	50 mg BID	100 mg BID	150 mg BID	200 mg BID	200/150 mg (AM/PM)	200/150 mg (AM/PM)
4a (when 2 nd week of Level 4 is not tolerated)	50 mg BID	100 mg BID	150 mg BID	200 mg BID	200 mg BID	200/150 mg (AM/PM)

Subjects will continue to adhere to the recommended fluid intake regimen outlined in [Section 5.8](#).

Subjects who tolerate their optimized dose will then enter the Maintenance Period during which time they will continue at the lixivaptan dose level achieved at the end of the Titration Period. During the Maintenance Period, the dose may be adjusted downward at the Investigator's discretion if needed to manage non-hepatic side effects and may also be increased back to the dose achieved at the end of the Titration Period. The Investigator may instruct the subject to hold the study drug for up to 7 days, if necessary, to manage acute intercurrent illness, tolerability issues, surgical procedures or life situations, e.g., airplane travel, etc. Additionally, subjects who have a longer interruption due to illness, including COVID-19, or other reasons may be able to re-start study drug when medically stable after discussion with the medical monitor and sponsor. Temporary or permanent study drug discontinuation for management of abnormal liver chemistry test results is described further in [Section 7.3.7](#).

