5.6 Treatment Compliance

Dispensing of study drug and reconciliation will be done at each visit during the Titration Period and every 4 weeks during the Maintenance Period. A final reconciliation will be done by the site once each subject completes study drug dosing. Subject compliance will be monitored by capsule counts as study drug is returned.

The dates of all study medication dosing, including interruptions, missed doses or overdose, must be recorded in the eCRF. If the subject is not $\geq 80\%$ compliant with the prescribed study drug doses during the study, then the period of non-compliance should be noted as significant protocol deviation and the Sponsor should be notified. The subject should be re-educated regarding the correct study drug doses to be administered. However, if the Investigator, medical monitor, and sponsor have agreed to a treatment interruption ([Section 5.2](#)), then this period of non-compliance will not be considered a protocol deviation.

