6.3 Titration Period

The Titration Period will last from 3 to 6 weeks. Subjects will self-administer lixivaptan at home. All subjects will start at Level 1 (50 mg BID) and will be increased weekly over 2-5 weeks through Level 2 (100 mg BID), Level 3 (150 mg BID), and Level 4 (200 mg BID), as necessary, according to the schedule described in Table 4. If aquaretic effects limit a subject's tolerability at Level 3 (150 mg BID) or Level 4 (200 mg BID), dose levels can be adjusted to Level 3a and Level 4a, respectively, which reduce the evening (PM) dose by 50 mg (from 150 mg to 100 mg for Level 3 to 3a, and from 200 mg to 150 mg for Level 4 to 4a). Titration will stop when a tolerable dose level is reached that achieves the goal of lowering trough (first morning, fasting except for water) urine specific gravity to ≤ 1.005 or the highest dose (Level 4 or 4a) is achieved (regardless of trough urine osmolality). The minimum dose to enter the Lixivaptan Maintenance Treatment Period is Level 2. Once tolerability and reduced trough urine specific gravity are achieved (or tolerability and maximum dose), subjects will stay on that dose for 1 additional week under most circumstances to confirm tolerability (Table 5). Subjects will then proceed to Visit 11/Last Titration Visit.

6.3.1 Visits 6 to 10

Visits 6, 7, 8, 9, and 10 will occur weekly ± 3 days *as needed* for titration and may be conducted remotely by a HHC. Subjects will either report to the clinic or interact with a HHC in the morning for their visits (after a minimum 8-hour overnight fast except for water) to undergo Titration Period assessments. Note that telemedicine will be utilized at these visits for the Investigator to assess the subject's status and tolerability of the study drug and to make a titration decision. Any other issues may also be discussed with the subject.

[figure not shown]
Subjects should bring into the clinic, or provide to the HHC, any remaining study drug. Remind the subjects not to take their morning dose of lixivaptan on the morning of the visit in order to obtain a trough PK sample should they advance to Visit 11 procedures.

The following procedures will be performed at each visit unless otherwise noted:

- Collect and review concomitant medication information
- Review study drug compliance/reconciliation
- Assess study drug tolerability by asking the subject, "Are you able to continue this dose for the next 12 months?"
- Review lab results from prior visit

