3 STUDY DESIGN

3.1 General Study Design

This is a Phase 3, open-label, repeat dose study designed to assess hepatic safety, non-hepatic safety, and efficacy of lixivaptan in subjects who previously experienced abnormal liver chemistry test results while treated with tolvaptan that resulted in permanent discontinuation of tolvaptan for that reason. Up to 50 subjects will be enrolled and treated. Evaluations will include frequent testing of liver chemistry tests (every week during the Baseline and Titration Periods, every 4 weeks during the Maintenance Period, and at the final Follow-up Visit), physical examinations, vital signs, safety labs (non-hepatic serum chemistry, hematology, and urinalysis), eGFR, urine osmolality determinations, and trough serum concentrations of lixivaptan. A deoxyribonucleic acid (DNA) sample to assess genetic variants associated with hepatic abnormalities (if and when feasible) will be obtained under a separate bio banking informed consent at Visit 5 or later in the study. After meeting study entry criteria during a 1-3-week Screening Period that can extend up to 8 weeks (in subjects who need adjustment of antihypertensive medications), subjects will enter a 3-week no-study-drug Baseline Period to obtain baseline serum creatinine measurements (for eGFR determinations) and repeat liver chemistry tests to assess baseline variability, followed by a 3-6 week Titration Period during which lixivaptan administered twice daily will be titrated to a dose that is tolerated and results in a reduced trough urine specific gravity (or until the maximum dose level is reached) as described below. The minimum dose to enter the Maintenance Period is Level 2 (100 mg twice per day (BID)). Treatment will continue for up to 52 weeks (12 months) after which study drug will be stopped, and final safety and efficacy assessments obtained during the Follow-up Period of 4 weeks. The maximum study duration will be 73 weeks (16.8 months). The study schematic is depicted in Figure 1.

Figure 1: Study Schematic

Screening Period (Visits 1, 2):

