7 STATISTICAL CONSIDERATIONS AND ANALYSIS

7.1 Derived General Variables

The below table (Table 4) provide the list of derived variables for demographic and baseline characteristics, various duration derivations, drug compliance, baseline derivations and other important derivations applicable for this study.

Variables	Formula					
Demographic characteristics						
Age at informed consent (in years)	Age = year of informed consent – year of birth					
BMI (kg/m ²)	weight (kg)/[height (m)] 2					
Derivation of Duration						
Study Duration (Days)	(Date of Last Visit – Date of informed consent) + 1					
Study day at any visit	Date of interest – date of first dose of study drug. One day is added if this difference is ≥ 0					
Adverse event duration (in days)	Event end date - Event onset date + 1.					
Duration of Exposure						
Duration of Exposure (days) in Titration Period	(Date of last administration of study drug – Date of first administration of study drug) +1, during the 6 week titration period					
Duration of Exposure (days) in Maintenance Period	(Date of last administration of study drug – Date of first administration of study drug) +1, during the 52 week maintenance period					
Treatment Compliance						
Treatment Compliance	(Total No. of capsules dispensed – Total No. of capsules returned)*50/total assigned dose*100 where, total assigned dose will be derived by sum of (AM+PM dose)*duration of this dose level for all different dosing levels					
eGFR Baseline and Fin	al Assessment Derivation (Appendix I)					
Baseline eGFR	Mean of 3 eGFR assessments (Visit 3, Visit 4 & Visit 5) obtained during the baseline period					
Final Assessment eGFR	Mean of 3 eGFR assessments (Visit 25, Visit 26 & Visit 27) obtained during the follow-up period					
Baseline Derivations						

Table 4: Derived Variables

Baseline	Latest non-missing measurement prior to first dose of study drug administration	
Change from baseline	Test Value at Post baseline value – Baseline Value	
Geometric Coefficient of Variation (CV%) for Pharmacokinetic data		
Geometric CV%	CV (%) =100× $\sqrt{\exp(\hat{\sigma}^2) - 1}$, where $\hat{\sigma}^2$ denotes the variance of the natural log-transformed values.	
	the natural log-transformed values.	

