8.5 Treatment Exposure and Compliance

8.5.1 Study Treatment Exposure

Total dose and duration of exposure for study drug (section 7.1) for titration period (period of 6 weeks) and maintenance period (period of 52 weeks), will be summarized using descriptive statistics by titration and maintenance period based on safety population.

A by subject listing of exposure will be presented based for the safety population.

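### SAP 7.1 and 8.5.1 count interruption days as days on drug, because duration of exposure is a first-to-last-dose span with nothing subtracted

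*SAP*

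**What the plan says.** SAP 7.1, in the table of derived variables, gives one duration formula per period: the last administration date minus the first, plus 1. The titration formula closes with "Date of first administration of study drug) +1, during the 6 week titration period" and the maintenance formula with "Date of first administration of study drug) +1, during the 52 week maintenance period". SAP 8.5.1 summarises total dose and this duration "for titration period (period of 6 weeks) and maintenance period (period of 52 weeks"). Neither section has a term for interruptions, and total dose is not defined.

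Both documents provide for drug-free time inside that span:

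- Protocol 5.2 and SAP 3.3.2 let the investigator hold drug for up to 7 days. They add that "subjects who have a longer interruption due to illness, including COVID-19, or other reasons may be able to re-start study drug", with no maximum length.
- Protocol 7.3.7.2 requires dose reduction or interruption above its transaminase or bilirubin thresholds. After an interruption it encourages restart, with exceptions, once tests have normalized or stabilized. It sets no maximum length either.

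The data needed to remove these days are collected. Protocol 5.6 states: "The dates of all study medication dosing, including interruptions, missed doses or overdose, must be recorded in the eCRF".

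On the length of titration, SAP 3.1 describes screening and baseline "followed by a 3-6 week Titration Period during which lixivaptan administered twice daily will be titrated", and Protocol 6.3 says "The Titration Period will last from 3 to 6 weeks".

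**The concern.** This is a hepatic safety study, and a low count of liver events means little without knowing how long subjects actually took the drug. A span that includes held days reports more time on drug than was studied, and nothing in the exposure definition tells the reader that this has happened.

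The point survives early termination. SAP Section 9 cuts the output to a limited set, but Appendix IV keeps Table 14.1.5.1, the Summary of Study Drug Exposure. The by-subject exposure listing promised in SAP 8.5.1 is not among the outputs in Appendix IV, and neither is a compliance summary table. Table 14.1.5.1 is thus the only remaining summary of time on drug.

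**Working it through.** The documents state no exposure figure to reproduce, so the check is date arithmetic on the SAP formula.

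**Inputs**
- Span formula: last dose − first dose + 1 (SAP 7.1).
- Full maintenance course: 52 weeks × 7 = 364 days (Protocol 6.4).
- Hold of up to 7 days (Protocol 5.2, SAP 3.3.2).
- Holds of 28 and 56 days, and a 90-day span for a subject who stops early: assumptions, since the documents give no such figures.
- Participants entering maintenance: 6 (SAP 9).

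**Step 1: size of the overstatement.** Let S be the SAP span and H the held days inside it that are followed by a restart in the same period. Days on drug = S − H, and the overstatement is H / (S − H).

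| Span S | Hold H | Days on drug | Overstatement |
|---|---|---|---|
| 364 | 7 (documents) | 357 | 7/357 = 2.0% |
| 364 | 28 (assumed) | 336 | 28/336 = 8.3% |
| 364 | 56 (assumed) | 308 | 56/308 = 18.2% |
| 90 (assumed) | 7 (documents) | 83 | 7/83 = 8.4% |
| 90 (assumed) | 28 (assumed) | 62 | 28/62 = 45.2% |

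**Step 2: effect on a group mean.** One 28-day hold among 6 subjects adds 28/6 = 4.7 days to the mean, whatever the spans are.

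**Step 3: when the formula adds nothing.** After a permanent stop there is no later dose, so the span ends at the last dose and H = 0. A hold that straddles the end of titration falls after the last titration dose and before the first maintenance dose, so neither period counts it.

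**Step 4: the six-week label.** The study maximum is 8 + 3 + 6 + 52 + 4 = 73 weeks, which matches the stated duration, so six weeks is the longest titration allowed. Applied to a subject's own first and last titration doses, the formula returns 21, 28, 35 or 42 days for 3, 4, 5 or 6 weeks. With no hold, that is correct in every case.

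**The case against.** The best defence is that a first-to-last-dose span is a coherent and reproducible definition and that nothing else depends on it. The primary and secondary hepatic endpoints are proportions of subjects with exact binomial intervals, and no person-time rate is planned. With 6 participants in maintenance, most of them terminated early, the retained drug accountability and drug tolerability/modification listings can be read subject by subject. The documents report no actual hold. All of this stands, and it limits the impact. It does not make the summary right: the listings let a reader look for holds but do not correct the table, and the span is not labelled as including them.

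Three stronger readings are tempting and not supported:

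- A reader might infer that titration exposure is fixed at six weeks, so that a three-week titrator is credited with 42 days instead of 21. The formula uses actual dose dates and returns 21. Even a literal 42-day window would only move dosed days from the maintenance row to the titration row. The total would rise only if those days were counted twice, which the SAP does not instruct.
- A reader might infer that the error is largest for subjects held for liver events. Protocol 7.3.7.2 allows dose reduction instead of interruption, a permanent stop adds no days, and non-hepatic interruptions are also uncapped. Liver holds are one route to a large overstatement and are not shown to be the largest.
- A reader might infer that reported exposure can only be too long. Uncounted interruptions do act in that direction. However, the date-imputation rules in SAP 7.2.1 label Visit 6 as the first dose date, whereas Protocol 6.2.3 has the first dose taken after Visit 5. If that label were carried into the exposure programming, titration would come out about 7 days too short.

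**Conclusion.** The point holds for interruptions. Followed as written, SAP 7.1 and 8.5.1 overstate days on drug for any subject who is held and restarted within the same period. The documented case is 2.0% (a 7-day hold in a full 364-day maintenance course). The 28-day figure of 8.3%, the 56-day figure and the 90-day rows rest on assumed lengths. Percentages grow as the hold lengthens or the course shortens, but whether any subject was held cannot be known from the plan.

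The impact is limited: no endpoint estimate changes, and few subjects are involved. The correction is still worth making, because the table is to be issued and describes time on drug in a study whose primary objective is hepatic safety. The six-week wording is a loose label that needs clarifying and does not by itself overstate total exposure.

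**What to change.** In SAP 7.1 and 8.5.1:

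1. Define days on drug, by period, as last dose date minus first dose date plus 1, minus the interruption days recorded in the eCRF within that period. Report this in Table 14.1.5.1.
2. Keep the present span as a second line labelled as including interruptions.
3. Define total dose as the sum, over dose levels, of the daily dose at that level times the days actually dosed at that level. The only dose sum the SAP now defines is the assigned dose in the compliance formula. If it were borrowed with span-based durations, it would carry the same error.
4. As a clarification, replace the six-week titration wording with each subject's own titration dates.

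The cost is SAP wording and minor programming on data already required in the eCRF. The small downside is that reported exposure becomes slightly shorter.

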6.2 Baseline Period

The 3-week Baseline Period begins at the conclusion of Visit 2 and consists of 3 visits – Visits 3, 4, and 5. It is designed to collect baseline data to record variability of each subject's liver chemistry test results and to obtain 3 serum creatinine values to determine baseline renal function (eGFR) according to the CKD-EPI equation. Visits will be weekly (Visits 3 and 4 may be done remotely if available), and no study drug will be administered during this time.

6.2.1 Visit 3

Prior to Visit 3 the eligibility review by the medical monitor will be completed for each subject. Subjects will either report to the clinic for Visit 3 or be scheduled for a remote visit with a HHC. The following procedures will be performed at Visit 3:

- Collect and review concomitant medication information
- Check SAEs
- Check vital signs (sitting blood pressure and heart rate)
- Collect a blood sample for the following laboratory testing:
 - Liver Chemistry Panel
 - Serum creatinine
- Contact the IRT to record the visit
- Schedule the subject for Visit 4 to occur in 1 week.

6.2.2 Visit 4

Subjects will either report to the clinic for Visit 4 or be scheduled for a remote visit with a HHC. The following procedures will be performed at Visit 4:

- Collect and review concomitant medication information

- Check SAEs
- Check vital signs (sitting blood pressure and heart rate)
- Collect a blood sample for the following laboratory testing:
 - Liver Chemistry Panel
 - Serum creatinine
- Contact the IRT to record the visit
- Provide the subject with a urine collection container and written instructions (See [Section 7.2.1](#) for more detailed information) to produce a first morning, fasting (8 hours except for water) spot urine specimen to be brought in at Visit 5 for specific gravity and U_{osm} determination.
- Schedule the subject to return to the clinic for Visit 5 to occur in 1 week.

6.2.3 Visit 5

Subjects will report to the clinic in the morning of Visit 5 (after a minimum 8-hour overnight fast) to complete the Baseline Period and begin the Lixivaptan Titration Period.

The following procedures will be performed at Visit 5:

- Collect and review concomitant medication information
- Check SAEs
- Check vital signs (Sitting blood pressure and heart rate)
- Measure body weight
- Process an aliquot of first AM spot urine for specific gravity
- Send the remaining AM spot urine for U_{osm} determination
- Collect urine to conduct a pregnancy test in WOCBP

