8.4.5 Clinical Laboratory Tests

Descriptive statistics (n, mean, standard deviation [SD], median, minimum, and maximum) for clinical laboratory data and changes from baseline will be presented for each scheduled time point.

The baseline value is the last value observed prior to first administration of study drug and any information taken after first administration of study drug is regarded as post-baseline

information. The change-from-baseline variables will be calculated as the post-baseline value minus the value at baseline. Change from baseline on continuous data will be summarized using descriptive statistics at each scheduled time point. For categorical data, change from baseline will be summarized using frequency and proportion at each scheduled timepoint.

Individual data listings of clinical laboratory results will be presented for each subject. Values outside of the clinical laboratory's reference range (i.e., those with low or high values) will be flagged in the clinical laboratory listings.

For all continuous clinical laboratory variables, a shift table comparing the baseline value (normal, low, and high) to last observation on treatment will be presented.

For urinalysis, a shift table comparing the baseline value to the maximum value will be presented (using number of subjects with results of negative, trace, or positive).

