After obtaining Informed consent, screening assessments will be performed at Visit 1 to determine subject eligibility. Subjects whose anti-hypertensive medications in the absence of diuretics are known and documented to have been stable (unchanged) for at least 3 weeks prior to Visit 1 may proceed to Visit 2 in 1 week to confirm eligibility. Subjects for whom the stability of anti-hypertensive medications in the absence of diuretics is unknown or not documented must be observed for 3 weeks during the Screening Period to ensure stable dosing of anti-

hypertensive medications then will be scheduled for Visit 2.. For those subjects who need to be discontinued from diuretic therapy and/or have their anti-hypertensive therapy optimized, the Screening Period may be extended up to a total of 8 weeks prior to Visit 2.

Subjects who meet all the inclusion criteria and none of the exclusion criteria and achieve stability of background anti-hypertensive medications in the absence of diuretics will return to the clinic for end-of-screening assessments at Visit 2, including body weight, vital signs, and a Complete Chemistry Panel (only if blood pressure medications were adjusted) at Visit 2 (which may be conducted remotely by a home healthcare clinician [HHC] with telemedicine to determine final eligibility). Eligible subjects will then enter the Baseline Period immediately at the completion of Visit 2. Subjects who fail inclusion/exclusion criteria because of temporary or correctable reasons may be re-screened up to 2 times after obtaining new informed consents with the approval of the medical monitor and sponsor.

Baseline Period (Visits 3 – 5): Following completion of all screening assessments and establishment of background medication stability, subjects will enter the 3-week no-study-drug Baseline Period during which time liver chemistry tests and serum creatinine (for eGFR calculation) will be assessed weekly to obtain baseline measurements and assess individual variability. Baseline trough spot urine specific gravity (as a point-of-care surrogate for urine osmolality) and U_{osm} will be determined only at Visit 5. Visits 3 and 4 may be conducted remotely by a HHC. At the successful completion of the Baseline Period (Visit 5), subjects will be dispensed study drug and begin treatment. This completes the Baseline Period and subjects will enter the Titration Period.

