 - Complete Chemistry Panel will be obtained at V1, V5, V11/Last Titration, V14, V17, V20, V24/ET, V27. If a subject required adjustment of blood pressure medications during Screening, then a repeat Complete Chemistry Panel will be performed at V2.
 - Liver Chemistry Panel will be obtained at V1, V3-V24/ET, and V27. If a subject requires adjustment of blood pressure medications during Screening, then a repeat Liver Chemistry Panel will be performed at V2.
 - Serum creatinine will be obtained at V3, V4, V25 and V26.
 - eGFR will be calculated and reported whenever serum creatinine is obtained either as part of the Complete Chemistry Panel or when serum creatinine alone is measured.
 - Hepatitis B surface antigen (HBsAg) and hepatitis C virus antibody (Anti-HCV) will be obtained at V1 only.

h Hematology blood samples will be obtained at V1, V5, V11/Last Titration, V17, V24/ET, and V27.

i First morning, fasting urine specific gravity and osmolality (AM trough) will be obtained at V5, at every visit during the Lixivaptan Titration Period (except V11/Last Titration) and at V24 and V27. Dispense container and review instructions (including not to take study drug on the morning of the next visit) with subject at V4-V9, V23, and V26.

Version: Final 1.0, Date: 01 Dec 2020 Page 19 of 42

- j Trough (7-10 AM prior to AM dose) plasma specimens for measurement of lixivaptan will be obtained at V5, at the final visit during the Titration Period (V11/Last Titration), and during the Maintenance Period *if* ALT levels >3 x ULN and/or total bilirubin >2 x ULN occur.
- k Utilizing a separate informed consent, all subjects will be asked to provide a DNA sample at the end of the Baseline Period (V5) to assess genetic variants associated with hepatic abnormalities (if and when feasible).

1 Serious adverse events (SAEs) will be collected throughout the study beginning with signing of informed consent. All non-serious adverse events will be collected beginning at the start of the Titration Period. Adverse Events of Special Interest (AESI) include hepatic events and pregnancy and will be reported on special forms using the SAE pathway of reporting.

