8.6.3 Analysis of Additional Hepatic Safety Endpoints

The proportion of subjects along with the exact binomial 95% CI who develop the following abnormalities during the Titration and Maintenance Periods will be tabulated and presented descriptively:

- >3 x, 5 x, >10 x, and 20 x ULN elevations for ALT
- >3 x, 5 x, 10 x, and 20 x ULN elevations for Aspartate aminotransferase (AST)
- >3 x, 5 x, 10 x, and 20 x ULN elevations for either ALT or AST
- ALT or AST levels >2 x their baseline
- Any elevation of total bilirubin (TBL) $>2 \times ULN$
- Any elevation of alkaline phosphatase (ALP) >2 x ULN
- Elevation of aminotransferase (>3 x ULN) accompanied by elevated bilirubin (>2 x ULN) will be evaluated using Drug-Induced Serious Hepatotoxicity (eDISH) plots
- Elevation of aminotransferase in temporal association with nausea, vomiting, anorexia, abdominal pain, or fatigue will be explored graphically using swimmer plots.
- Possible liver-related deaths and liver-related treatment discontinuations.

The liver dysfunction occurring during the titration and maintenance period judged using the Drug Induced Liver Injury Network (DILIN) (Appendix II) probability criteria independently by investigator and HERC will be listed separately.

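### The endpoint of ALT or AST above twice baseline rests on one pre-dose value although three weekly baseline panels are collected, which adds false flags; the size depends on a variability the documents do not give

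*SAP*

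**What the plan says.** The general baseline in SAP 7.1 (Table 4, derived variables) is the "Latest non-missing measurement prior to first dose of study drug administration". Protocol 8.4.5 has the same rule for laboratory data: "The baseline value is the last value observed prior to first administration of study drug".

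SAP 8.6.3 lists "ALT or AST levels >2 x their baseline" among the additional hepatic endpoints, to be summarised as "The proportion of subjects along with the exact binomial 95% CI who develop the following abnormalities". SAP 8.7.2.1 uses the same category when relating liver tests to trough drug levels. Neither section gives this item its own baseline, so the general rule applies. The first dose follows Visit 5 (protocol 6.2.3), so the denominator is normally the Visit 5 result alone.

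More data are available. The notes to the SAP's schedule of procedures state that the "Liver Chemistry Panel will be obtained at V1, V3-V24/ET, and V27". Protocol 6.2 describes the three-week Baseline Period as "designed to collect baseline data to record variability of each" subject's liver tests, and SAP 3.1 says that "liver chemistry tests and serum creatinine (for eGFR calculation) will be assessed weekly to obtain baseline measurements and assess individual variability". For creatinine the plan uses all three visits: baseline eGFR in SAP 7.1 is the "Mean of 3 eGFR assessments (Visit 3, Visit 4 & Visit 5) obtained during the baseline period".

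**The concern.** The endpoint asks whether any of many on-treatment values exceeds twice a single reference value. If the Visit 5 result happens to be low, ordinary later values can look like a doubling. If it happens to be high, a real rise can go uncounted. Averaging three values reduces both errors, and the three values are collected for this purpose. The SAP gives no reason for averaging eGFR and not ALT or AST.

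The trial has no control arm to show how many flags arise without the drug. The protocol itself (7.3.7.2) acknowledges background variability of liver tests in ADPKD. A count inflated by a noisy denominator could therefore be read as a drug signal.

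**Working it through.** The documents state no false-positive rate and no within-subject variability for ALT or AST, so there is no figure of the plan's to reproduce. The check asks how many subjects would be flagged if the drug had no effect.

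**Inputs from the documents**
- Baseline panels: Visits 3, 4 and 5.
- On-treatment panels: 3 to 6 in titration (protocol 6.3), plus Visits 12 to 24 in maintenance (protocol 6.4), which is 13. Total 3 + 13 = 16 to 6 + 13 = 19.
- Up to 50 subjects (SAP 5).

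**Assumptions**
- Log-normal values with constant within-subject CV, so the log-scale SD is s = √ln(1 + CV²).
- Independent errors between visits, relaxed below.
- Correlation of 0.5 between ALT and AST at the same visit.

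**Step 1: one analyte, one visit.** The log ratio of a new value to a single baseline has SD s√2. Against a geometric mean of three, the SD is s√(1 + 1/3) = s√(4/3). The chance of exceeding 2 is 1 − Φ(ln 2 / SD).

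| CV | s | Single value | Mean of three |
|---|---|---|---|
| 20% | 0.198 | 1 − Φ(2.475) = 0.67% | 1 − Φ(3.031) = 0.12% |
| 25% | 0.246 | 1 − Φ(1.991) = 2.33% | 1 − Φ(2.438) = 0.74% |
| 30% | 0.294 | 1 − Φ(1.670) = 4.75% | 1 − Φ(2.045) = 2.04% |

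**Step 2: one analyte, any of 19 visits.** All 19 comparisons share one denominator. If its standardised log error is z, the chance of no flag is Φ(ln 2 / s + z)^19. The flag rate is therefore 1 − E[Φ(ln 2 / s + z)^19], with z standard normal. Numerical integration gives 7.3%, 19.4% and 32.1% at CV 20%, 25% and 30%. Simulation (400,000 subjects per scenario) gives 7.25%, 19.43% and 32.27%. With the arithmetic mean of three, simulation gives 1.79%, 9.27% and 21.46%.

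**Step 3: the endpoint as written, ALT or AST, any of 19 visits** (simulation, single value against arithmetic mean of three).

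| CV | Single | Mean of three | Ratio | Expected in 50 subjects |
|---|---|---|---|---|
| 15% | 1.46% | 0.09% | about 16 | 0.7 vs 0.04 |
| 20% | 12.88% | 3.45% | 3.7 | 6.4 vs 1.7 |
| 25% | 31.28% | 16.29% | 1.9 | 15.6 vs 8.1 |
| 30% | 47.82% | 34.70% | 1.4 | 23.9 vs 17.4 |
| 40% | 68.99% | 63.85% | 1.1 | 34.5 vs 31.9 |
| 50% | 79.53% | 78.60% | 1.0 | 39.8 vs 39.3 |

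At CV 10% both rates are about zero.

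**Step 4: sensitivity**, at CV 20%, 25% and 30% in that order.
- 16 panels instead of 19: 11.5% vs 2.9%, 28.9% vs 14.4%, 45.1% vs 31.3%.
- Serial correlation 0.3 between consecutive values: ratios 2.4, 1.5 and 1.25.
- Serial correlation 0.6: ratios 1.6, 1.3 and 1.15.
- Geometric instead of arithmetic mean of three: ratios 3.2, 1.7 and 1.2, falling to 0.94 at CV 50%.

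The single value never gave fewer false flags than the arithmetic mean of three. The size of the excess depends mainly on the CV, and then on serial correlation.

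**The case against.** **Scope.** The primary and secondary hepatic endpoints use ALT multiples of ULN with attribution by the hepatic review committee (SAP 4.1, 4.2.1). Retesting and dose action are also triggered by ULN multiples (protocol 7.3.7). None of this depends on the baseline rule. The affected item is one of nine additional endpoints, and no hypothesis test is planned (SAP 8.6). This stands.

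**Early termination.** SAP section 9 reports that only 6 participants entered maintenance and that no statistical analyses will be done. Appendix IV keeps one hepatic summary table, for the primary and secondary endpoints (14.3.2.1). Liver chemistry is listed by subject (16.2.8.1.3), so a reader could compute either baseline. This stands too. However, the baseline disease characteristics table (14.1.2.2.1) and the listing of baseline ALT, AST and bilirubin (16.2.4.2.2) are retained, so the definition remains in use.

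**A defensible convention.** Last value before dosing is a common rule, and the protocol and SAP agree on it. It is not an inconsistency between documents. The eGFR analogy is also imperfect, because eGFR averages three values at both ends while ALT and AST are judged visit by visit. But convention does not explain leaving Visits 3 and 4 out of the denominator when they were scheduled to establish baseline and variability.

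**Masking is bounded.** Exclusion 17 bars ALT or AST above 1.5 x ULN during Screening or Baseline. In a subject who meets it, twice baseline is at most 2 × 1.5 = 3 x ULN, so a rise above 3 x ULN is flagged under either definition. Only smaller rises can be hidden.

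**Stronger readings.** A reader might infer that the rule roughly doubles false positives. That holds only near CV 25% with independent errors, or between CV 20% and 25% with modest serial correlation, and the documents give no CV. A reader might also infer that the count is largely noise. Without a CV this cannot be shown. At high CV most false flags come from taking the maximum over up to 19 visits, which averaging the baseline does not cure: at CV 30% the mean of three still flags 34.7%.

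**Conclusion.** The point holds as a narrow analysis choice worth changing. The rule leaves two of the three baseline panels out of the reference value for the one liver endpoint defined against baseline, and it adds false flags. Under the stated assumptions the share falls from about 13% to 3% at CV 20%, from 31% to 16% at CV 25%, and from 48% to 35% at CV 30% when the mean of three is used. The direction is secure against an arithmetic mean. No single multiplier is, because the CV, the error structure and the ALT-AST correlation are all assumed.

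The documents do not support reading this as a threat to the trial's main hepatic conclusion. The practical effect on what will be reported is small.

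**What to change.** In SAP 7.1, define baseline ALT and AST for the twice-baseline endpoint (8.6.3, and its reuse in 8.7.2.1) as the mean of the available Visit 3, 4 and 5 values. Using whatever values are available matches the rule for eGFR in SAP 7.2.2. If the team prefers to keep the last value as the main definition, add the three-visit mean as a sensitivity summary.

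Record the departure from protocol 8.4.5 in SAP section 9. Protocol 8.7 lets the SAP modify planned analyses and calls for an amendment only for major changes to the primary analysis, which this is not. State which definition the retained baseline table and listing use.

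Bilirubin and ALP need no change, because their items in SAP 8.6.3 are multiples of ULN.

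The cost is one derivation line, one entry in section 9 and a label on the retained outputs. No new data are needed.
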